Faba beans are a rich source of protein, vitamins, minerals and dietary fibre, and are low in fat. They are vegan, genetically modified organism (GMO) free and free of common allergens. Faba bean has a well-balanced amino acid profile, similar to that of the pea and soy (see Table 1) (16). Clinical studies have shown that regular consumption of pulses (including faba beans) can reduce blood levels of total cholesterol and low-density lipoprotein (LDL), and therefore may reduce the risk of CVD. One of the key benefits of FPs over many other plant-based protein powders, including pea protein, is that it has a less grainy (creamier) texture and is more palatable. Overall, there is very little known about the basic digestion of FP in terms of the postprandial amino acid profile and its effect on metabolism after ingestion. This information is fundamental to understand before embarking on longer term human studies. To the best of our knowledge, no other study has examined the specific bioavailability, digestibility, and metabolism of FP compared to WP.

AIM

The aim of this study is to assess the acute effect of FP vs WP, with and without a glucose load, on satiety hormones, postprandial amino acid bioavailability, glucose, insulin and a range of metabolomic markers in circulating blood in healthy volunteers.

MAIN RESEARCH QUESTIONS AND HYPOTHESES BEING ADDRESSED

Question 1 – What effect does FP have on glucagon-like peptide-1 (GLP-1), other satiety hormones, amino acid availability, glucose, insulin and a range of metabolomic markers compared to the same dose of WP in healthy adults?

Hypothesis 1 – A beverage containing FP protein will have a similar stimulatory effect on GLP-1 and satiety hormone secretion but will have lower amino acid availability compared to WP.

Question 2 – What effect does FP together with a glucose load have on GLP-1 and other satiety hormones, amino acid availability, postprandial glycaemic, and insulinaemic response and a range of

metabolomic markers compared to the same dose of WP together with a glucose load in healthy adults?

Hypothesis 2 – A beverage containing FP and glucose will attenuate the postprandial glycaemic response to a greater extent than a beverage containing the same dose of WP and glucose.

STUDY DESIGN OVERVIEW

The study is a single-blind, randomised, acute, crossover intervention trial.

STUDY DESIGN

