Compared to a 50g glucose control, Thondre et al. showed that there was a dose response effect of pea protein (25g and 50g) on postprandial glycaemia and stimulated insulin release over a three hour period in healthy adults (14).

RANDOMISATION AND BLINDING

The study will be a four-visit, single-blind, acute crossover study; with at least a one week washout period between visits. A computer-generated randomisation scheme will be prepared by a statistician who is independent of the study team and provided to the researcher who is preparing the test beverages (CK).

The researcher will prepare beverages for each visit for each participant according to the randomisation list. To maintain participant blinding, beverages will be provided in identical opaque containers labelled with the participant number and the intervention period. Thus, the participants will be unaware which beverage they are taking during each visit.

PROPOSED OUTCOMES

Primary endpoint: Circulating concentrations of intact GLP-1 in blood.

Secondary endpoints: Circulating concentrations of other satiety hormones, glucose and insulin concentration, amino acid availability in blood.

Exploratory endpoints: Metabolomic and proteomic markers in blood.

SAMPLE SIZE

Based on variability data from previously published studies in similar populations (6, 8), as well as unpublished data from our own group, a sample size of 16 participants will give the study 80% power to detect a significant difference of 10-15% in total AUC GLP-1 between treatment conditions (WP vs FB; or WPG vs FPG) or a difference in AUC Glucose of 5-15% between treatment conditions (WPG vs FPG).

To allow for dropout, it is anticipated that 20 participants will be recruited.

STUDY ASSESSMENTS

All assessments will be carried out at the Northern Ireland Clinical Research Facility, U Floor, Belfast City Hospital tower block.

Questionnaires (paper copies provided for completion):

All participants will be asked to complete a short lifestyle questionnaire (sex, age, food and drinks, alcohol, physical activity and smoking status (adapted from Leeds Short Form Food Frequency Questionnaire (20)); see Appendix 8.0) at their first visit.

Visual analogue scales (see Appendix 9.0) to rate feelings of hunger will be completed during each study visit at T0 (before the drink is consumed), T30, T60, T90 and T120 (minutes).

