Primary and secondary endpoints will be analysed using repeated measures ANOVA (for normally distributed data) and non-parametric Friedman test (where data were not normally distributed) to compare concentrations at each time point. Incremental Area under the Curve (iAUC) (at 30, 60, 90 and 120 min) will be calculated and reported along with peak concentration and time of peak concentration for relevant endpoints in response to each of the interventions. Post hoc analyses will be performed using the Bonferroni correction for parametric data and the Wilcoxon signed-rank test for non-parametric data. Statistical significance will be set at p value ≤ 0.05 for all tests.

Metabolomic and proteomic analysis will be considered exploratory analysis. P-values will not be altered for multiple testing, but findings will be treated as hypothesis generating rather than hypothesis testing.

PROPOSED TIMELINE FOR THE STUDY

January – February 2024 – Obtain ethical approval; study set-up

February – March 2024 – Recruitment

February – June 2024 – Completion of dietary interventions

July-December 2024 – Laboratory analysis, statistical data analysis and write-up

STUDY PHONE NUMBER AND EMAIL ADDRESS

To ensure personal telephone numbers are not given out we have obtained a mobile phone unique to the study.

Contact information for study participants:

Email address: [contact] or [contact]

[contact]

ETHICAL CONSIDERATIONS

The study will be carried out in accordance with the declaration of Helsinki. Ethical approval will be obtained from the Faculty of Medicine, Health and Life Sciences Research Ethics Committee at Queen's University Belfast. Participants will be given full details of the study and will have the opportunity to ask questions. All participants will provide written informed consent prior to participation and will be informed that they can withdraw from the study at any time without having to give a reason. Participants will be informed that any data or samples provided up to the point of withdrawal may be included in the study unless they request otherwise. Participants can also request withdrawal of their data or samples at any time after completion of the study by contacting the Chief Investigator; any data or samples that have been analysed or reported at the time of request will not be able to be retracted.

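### Hypothesis 1 predicts a similar GLP-1 effect of faba bean and whey protein, but the sample size and every named test address only a difference, so the plan has no valid route to support that prediction.

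*Protocol*

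**What the plan says.** - **Hypothesis.** In the section on main research questions and hypotheses, Hypothesis 1 reads: "A beverage containing FP protein will have a similar stimulatory effect on GLP-1 and satiety hormone secretion". The same sentence then predicts lower amino acid availability than with whey protein (WP). The first half is a statement of similarity, the second a directional difference.
- **Endpoint.** Under Proposed Outcomes: "Primary endpoint: Circulating concentrations of intact GLP-1 in blood".
- **Sizing.** Under Sample Size: "a sample size of 16 participants will give the study 80% power to detect a significant difference of 10-15% in total AUC GLP-1". This covers both whey against faba bean protein (FP) and the same comparison with glucose. No SD is given; the section names only its sources. It adds: "To allow for dropout, it is anticipated that 20 participants will be recruited".
- **Analysis.** Under Statistical Analysis, primary and secondary endpoints go to repeated measures ANOVA or, if not normally distributed, to the Friedman test. Post hoc comparisons use Bonferroni or Wilcoxon signed-rank. The only decision rule is: "Statistical significance will be set at p value ≤ 0.05 for all tests".

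The protocol nowhere defines similar, and it states no equivalence or non-inferiority margin and no rule based on a confidence interval.

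**The concern.** A test of no difference has two outcomes. If it is significant, it contradicts the GLP-1 half of Hypothesis 1. If it is not significant, it leaves the question open, because a real difference may have been missed. Neither outcome supports similarity.

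The hypothesis on the primary endpoint therefore has no planned analysis that could confirm it. If similarity were nevertheless concluded from p > 0.05, the incentive would run the wrong way: noisier assays, missing samples and more dropouts all make non-significance more likely, so poorer data would appear to favour the hypothesis.

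**Working it through.** **Inputs.** From the protocol: 16 participants for 80% power, a detectable difference of 10-15% in total GLP-1 AUC, significance level 0.05, 20 recruited. Each participant takes all four drinks, so WP against FP is a paired comparison. Assumed, because not stated: a two-sided paired t-test on AUC, with differences expressed as a percentage.

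**1. The protocol's own figure.** Without an SD, n = 16 cannot be reproduced independently. It can only be solved backwards. With df = 15 and critical t = 2.131, the noncentral t distribution gives 80% power when δ/SD = 0.749 (noncentrality 0.749 × √16 = 3.00). Hence:

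- 10% difference: SD of within-participant differences = 10/0.749 = 13.3%
- 15% difference: SD = 15/0.749 = 20.0%

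Recruiting 20 for 16 completers matches a 20% dropout allowance (16/0.8 = 20).

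**2. What a non-significant result would mean.** Probability of p > 0.05 with 16 completers:

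| True difference | SD | Noncentrality | P(non-significant) |
|---|---|---|---|
| Full detectable size (10% or 15%) | 13.3% or 20.0% | 3.00 | 20% |
| Half of it (5% or 7.5%) | 13.3% or 20.0% | 1.50 | 71% |
| 7.5% | 13.3% | 2.25 | 44% |
| 10% | 20.0% | 2.00 | 54% |

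With 12 completers instead of 16, a true 10% difference at SD 13.3% is missed 34% of the time rather than 20%.

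The expected half-width of the 95% confidence interval at n = 16 is 2.131 × SD/√16, that is 7.1 points (SD 13.3%) to 10.7 points (SD 20.0%). A non-significant result would therefore often be compatible with differences close to those the trial was sized to detect.

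**3. What a test of similarity would deliver.** Two one-sided 5% tests are the same as requiring the 90% confidence interval to lie inside ±margin. The protocol states no margin, so its 10-15% is used here for illustration only:

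| Margin and SD | True difference | Power, 16 | Power, 17 | Power, 20 | Completers for 80% |
|---|---|---|---|---|---|
| Margin = detectable difference, matching SD | 0 | 78% | 81% | 89% | 17 |
| Same | 30% of margin | 62% | 65% | 73% | 24 |
| Margin 10%, SD 20.0% | 0 | 23.5% | 27% | 39% | 36 |
| Margin 15%, SD 13.3% | 0 | 99% | 99% | over 99% | 9 |

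The answer depends heavily on the margin, the SD and the true difference, none of which the protocol fixes for this purpose.

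**The case against.** The best defence is that Question 1 is open (what effect does FP have compared with WP), that the Aim is to assess the acute effect of one protein against the other, and that Hypothesis 1 is a scientific expectation in a first study of a little-known protein. On that reading a two-sided difference test answers the question asked, and the planned means, SDs, iAUC and peak values give the reader more than a p-value. The SAP is also not shown and could contain an interpretation rule.

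Part of this stands. A reader might infer that the investigators will take p > 0.05 as proof that FP is like WP. The protocol does not say so, and the point does not rest on it. Difference testing is right for the amino acid half of Hypothesis 1 and for Hypothesis 2, and the sample-size section also serves the glucose pair, so sizing on a difference is not wrong for the trial as a whole.

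The error rates above are also not those of the exact planned test. They rest on a back-solved SD and a paired t-test on AUC, whereas the Statistical Analysis section compares concentrations at each time point. The 54% figure pairs the larger SD with the smaller difference, which is the unfavourable corner.

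What does not stand is the appeal to the SAP. This document already fixes the hypothesis, the basis of sizing, the tests and one significance rule for all of them, and these do not fit together.

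**Conclusion.** The mismatch holds. It concerns the primary endpoint and is confined to the GLP-1 and satiety-hormone half of Hypothesis 1: followed as written, the plan cannot support that prediction. Under the assumptions shown, a true GLP-1 difference of 5-7.5% would go undetected about 71% of the time, so a non-significant result would carry little evidence of similarity.

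Three stronger readings are tempting, and the document supports none of them:

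- **That 16 is far too few to show similarity.** With a margin equal to the detectable difference and no true difference, 17 completers give 80% power.
- **That the repair certainly needs no extra participants.** Power at 16 is 78% in that favourable case, 62% if the true difference is 30% of the margin, and about 23% with SD 20% and a 10% margin. The 89% at 20 assumes that nobody drops out.
- **That the protocol's 15% is a ready-made margin.** The 10-15% is described as detectable, not as negligible.

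**What to change.** Choose one of two routes before any GLP-1 results are seen.

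**(a) Reword.** State the GLP-1 and satiety-hormone part of Hypothesis 1 as a difference or estimation question. Report the FP-WP difference or ratio in GLP-1 AUC with its confidence interval whatever the result, and add that a non-significant test is not evidence of similarity. The present sizing basis then fits the hypothesis.

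**(b) Keep similarity.**

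- Pre-specify a margin and justify why a difference of that size would not matter.
- Name the GLP-1 AUC measure to which it applies. The Sample Size section uses total AUC and the Statistical Analysis section uses incremental AUC. The two must be reconciled, because total AUC includes the fasting level, which pulls a ratio towards 1 and makes similarity easier to conclude.
- Conclude similarity only if the 90% confidence interval lies inside the margin.
- State the power with its SD, margin and assumed true difference.

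Route (a) costs a few sentences. Route (b) costs wording, one scientific judgement on the margin and a less favourable stated power, and it may need more completers if a tight margin is chosen or the SD is at the upper end. Neither route changes the visits or the sampling.

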RESEARCH PROTOCOL

TITLE

Effect of faba bean protein versus whey protein on human metabolic responses: a single-blind, randomised, acute, crossover study

SHORT TITLE (USED ON PARTICIPANT FACING DOCUMENTS)

Digestibility of broad bean (faba bean) protein compared to whey protein

BACKGROUND

Protein is the key provider of essential amino acids (EAA) required by the body for growth, repair and maintenance of bone, teeth, muscle and tissue, and for the production of functional components such as hormones, enzymes and immunoglobulins. Unlike carbohydrate and fat which can be stored within the body, daily dietary protein is essential to maintain the correct levels of amino acids for optimum health and to support growth.

Protein in the diet is derived from animal and plant sources and, with an increased focus on wider issues within the food system such as environmental sustainability, land-use and biodiversity, there has been increased focus on examining the role of different protein sources in promoting health. Protein quality, such as digestibility, bioavailability, absorption, EAA content, and the anabolic effect of dietary proteins can vary by source (1). The amino acid content of some common plant proteins (soy, pea and faba bean) compared to whey protein are shown in Table 1.

Table 1: Amino acid content of various dietary protein sources (g/100g raw material).

| | Whey | Soy | Pea | Faba bean |
|--|--------------|--------------|--------------|------------------|
| Essential Amino Acids (EAA) (g/100g) | | | | |
| Threonine | 5.4 | 2.3 | 2.5 | 2.9 |
| Methionine | 1.8 | 0.3 | 0.3 | 0.7 |
| Phenylalanine | 2.5 | 3.2 | 3.7 | 4.0 |
| Histidine | 1.4 | 1.5 | 1.6 | 2.1 |
| Lysine | 7.1 | 3.4 | 4.7 | 5.4 |
| Valine | 3.5 | 2.2 | 2.7 | 4.3* |
| Isoleucine | 3.8 | 1.9 | 2.3 | 3.9* |
| Leucine | 8.6 | 5.0 | 5.7 | 7.1* |
| Sum of EAA | 34.1 | 19.9 | 23.6 | 30.4 |
| Non-essential amino acids (NEAA) (g/100g) | | | | |
| Serine | 4.0 | 3.4 | 3.6 | 4.2 |
| Glycine | 1.5 | 2.7 | 2.8 | 3.2 |
| Glutamic acid | 15.5 | 12.4 | 12.9 | 14.8 |
| Proline | 4.8 | 3.3 | 3.1 | 3.8 |
| Cysteine | 0.8 | 0.2 | 0.2 | 0.8 |
| Alanine | 4.2 | 2.8 | 3.2 | 3.6 |
| Tyrosine | 2.4 | 2.2 | 2.6 | 3.0 |
| Arginine | 1.7 | 4.8 | 5.9 | 7.6 |
| Aspartic acid | Not measured | Not measured | Not measured | 8.7 [#] |

| | | | | |
|-------------|------|------|------|------|
| Sum of NEAA | 34.9 | 31.9 | 34.4 | 41.0 |
|-------------|------|------|------|------|

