Values for whey, soy and pea are presented in g per 100g raw material. Whey, soy and pea values provided by Gorissen et al (1) which did not report tryptophan, aspartic acid, asparagine, and glutamine were not measured. Faba bean values, provided by Pulsin manufacturer, are reported as Average Amino Acid Composition [(*=Branch chain amino acids (BCAA)g/100g Powder]. #Not included in Sum of NEAA, as not available for other protein sources.

Animal proteins, such as milk or whey protein, are recognised as high biological value or 'complete' proteins as they provide all the EAA needed by the human body, have high digestibility, and can help transport other important nutrients such as calcium and iron. Proteins from animal sources (dairy, meat, fish, poultry) are the most bioavailable sources. Whey protein (WP) is widely used as an ingredient in foods or as a food supplement owing to its high nutritional value and versatility. WP is a high biological value protein, containing all the EAA, including the essential and is rich in branched chain amino acids (BCAA) leucine, isoleucine and valine, as well as bioactive peptides that are rapidly absorbed into the circulation. The digestibility and metabolic effects of WP have been widely studied in acute and some longer-term studies. In acute studies, it is known to stimulate the secretion of gut hormones (incretin peptides), particularly glucagon-like peptide-1 (GLP-1) and gastric inhibitory polypeptide (GIP) which stimulate insulin secretion (2-4). The release of incretin peptides regulates the rate of gastric emptying and gastrointestinal transit of food (2-4). GLP-1 stimulates glucose-induced insulin secretion and reduces postprandial glycaemia. An increase in levels of GLP-1 can increase the synthesis of insulin stores in beta cells, increase beta cell mass and reduce the rate of beta cell apoptosis (5). Insulin can regulate hepatic glucose production and cross the blood brain barrier and may suppress appetite. WP is commercially available and often used to supplement a healthy diet. It has received much attention for muscle building, due to its high level of leucine, which acts as a signal to initiate the process of muscle protein synthesis. WP supplementation may serve as a simple, non-pharmaceutical method to improve postprandial glycaemia for health participants and those with T2DM (6-8).

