Participants will complete four acute interventions (two pairs, as shown in Table 2 below) in a random order with at least a one week washout between studies (four study visits in total, each visit will last 2.5 hours). At each visit, participants will consume one of the four test beverages detailed in Table 2.

Table 2 Details of the four acute interventions provided to participants (one per study visit; four study visits in total)

[figure not shown]
| | | |
|------------------------|----------------|---|
| Pair 1 (WP vs FP) | Intervention 1 | Whey protein, WP; 0.4g/kg body weight |
| | Intervention 2 | Faba bean protein, FP; 0.4g/kg body weight |
| Pair 2 (WPG vs FPG) | Intervention 3 | Whey protein and glucose load, WPG; 0.4g/kg body weight WP + 50g glucose |
| | Intervention 4 | Faba bean protein and glucose load, FPG; 0.4g/kg body weight FP + 50g glucose |

An overview of the study assessments and the participant's journey through the study is shown in Figure 1 and a detailed description of the methods is given below.

In brief, the study will require participants to attend the Northern Ireland Clinical Research Facility (NICRF) at the Belfast City Hospital U-floor on four occasions at least one week apart (Visits 1,2,3,4); each of these visits will last 2.5 hours and participants will consume a beverage consisting of one of the above interventions at each visit.

Figure 1: Overview of participant's journey throughout the study

Four interventions will be delivered in random order: intervention #1 - WP; intervention #2 - FP; intervention #3 – WPG; intervention #4 – FPG.

PARTICIPANTS

A total of 20 healthy participants will be recruited (see sample size section for details). The specific inclusion and exclusion criteria are as follows:

Inclusion criteria

- 18-40 years old
- Healthy volunteers
- Body mass index (BMI) $\geq 18.5 \text{ kg/m}^2$ and/or weight $\geq 50\text{kg}$ (7 Stone 12 pounds) [minimum weight in line with NI Blood transfusion requirements]
- Be willing to consume WP and FP beverages
- Be available to meet the requirements of the study

Exclusion criteria

- Medical condition or medication known to affect glucose regulation or appetite and/or digestion and absorption of nutrients
- Known history of diabetes mellitus or the use of antihyperglycemic drugs or insulin to treat diabetes and related conditions
- Use of steroids, protease inhibitors or antipsychotics

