At the end of each visit, participants will be asked to complete an assessment of palatability of the test beverage they consumed (see Appendix 10.0). Using the 9 point hedonic scale (21), we will ask participants to rate the initial and after taste, the texture/feeling in their mouth, and the overall acceptability of the beverage.

Anthropometric data:

At the first visit, weight (kg) and height (m) will be measured using calibrated scales and a stadiometer respectively (see Appendix 11.0). Body mass index (BMI) will be calculated – weight in kilograms divided by height in meters squared.

Waist circumference (inches) will be measured using standard equipment (See Appendix 11.0). It will be measured using a flexible measuring tape designed for this purpose.

Blood samples:

At the start of each visit to the NI Clinical Research Facility, a cannula will be inserted by a trained nurse. Blood samples will be taken at T0 (before the drink is consumed), T30, T60, T90 and T120 (minutes). At each time point, a 4ml EDTA plasma, 2ml Sodium Fluoride plasma and 6ml Serum tube will be collected giving a total volume of 60mls for each study visit.

Participants will be supervised at all times by the research nurse taking the blood samples and the researcher. They will be asked to remain in the NICRF for 15 minutes after the last blood sample has been taken.

All blood samples will be taken from the antecubital vein by the trained nurse at NICRF. Samples will be separated into plasma and serum and stored at -80°C for batch analysis once the study has been completed. Samples will be processed, stored and analysed in the nutrition labs at the Centre for Public Health (CPH).

Participants will be given a snack and a drink to take away at the end of study visit.

LABORATORY METHODOLOGY (Nutrition laboratories, Centre for Public Health)

Assessment of gut hormones

The assessment of gut hormones will be measured by enzyme-linked immunosorbent assay (ELISA). GLP-1 will be carried out using an ELISA kit purchased from EMD Millipore Corporation. Other gut hormones (including GIP, Leptin, Ghrelin and Adiponectin) will be measured by Quantikine ELISA kits (R&D Systems, Minneapolis, MN, USA) as per the manufacturer's instructions. In assay validation, multiple freeze/thaw cycles will be tested

for stability. All assays were performed in duplicate using kits with the same batch number, by operators blinded to sample identity.

Assessment of insulin and glucose levels

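### Amino acid *availability* is claimed from blood taken over two hours only, so a lower faba bean area could reflect slower appearance, less complete absorption or lower essential amino acid content

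*Protocol*

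**What the plan says.** The short title of the protocol is "Digestibility of broad bean (faba bean) protein compared to whey protein". The aim lists "postprandial amino acid bioavailability" among the effects to be assessed. Questions 1 and 2 both ask about amino acid availability, and Hypothesis 1 predicts that a faba bean beverage "will have lower amino acid availability compared to WP". Under Proposed Outcomes, amino acid availability in blood is a secondary endpoint, with no further definition.

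On measurement, the Blood samples paragraph says: "Blood samples will be taken at T0 (before the drink is consumed), T30, T60, T90 and T120 (minutes". The Study Design section says that "each visit will last 2.5 hours", which leaves no room for later samples. The Statistical Analysis section compares concentrations at each time point and calculates an incremental area under the curve (iAUC) at 30, 60, 90 and 120 minutes. This is to be "reported along with peak concentration and time of peak concentration for relevant endpoints".

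On speed, the Background credits whey with "bioactive peptides that are rapidly absorbed into the circulation" and says that incretins regulate gastric emptying and transit. It also says that very little is known about the basic digestion of FP.

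**The concern.** Availability, bioavailability and digestibility are naturally read as extent: how much of the protein's amino acids reaches the circulation. An area cut off at 120 minutes depends on both rate and extent. If one protein enters the blood later but just as completely, part of its area falls after the last sample and is lost.

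A smaller FP area would match the prediction in Hypothesis 1 whichever cause produced it. The report could then say that FP supplies fewer amino acids when the data show only that fewer had appeared by two hours. If a curve is still rising at T120, the highest sampled value is neither the true peak nor its true time, but the plan would report it as both.

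**Working it through.** **What the documents supply.** They give the sampling times (0, 30, 60, 90, 120 min) and Table 1. They give no amino acid effect size, standard deviation or kinetic parameter, so there is no stated figure to reproduce. Every kinetic value below is an assumption.

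**Step 1: content.** The Table 1 sums reproduce: whey 5.4 + 1.8 + 2.5 + 1.4 + 7.1 + 3.5 + 3.8 + 8.6 = 34.1; faba 2.9 + 0.7 + 4.0 + 2.1 + 5.4 + 4.3 + 3.9 + 7.1 = 30.4. The ratio per 100 g is 30.4/34.1 = 0.89. As a share of all amino acids summed in the table, the figures are 30.4/(30.4 + 41.0) = 0.426 and 34.1/(34.1 + 34.9) = 0.494, a ratio of 0.86. Either way, a lower essential amino acid area could arise from content alone. For single amino acids the direction varies: leucine is 7.1 against 8.6, valine 4.3 against 3.5.

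**Step 2: timing, with total absorption held equal.** Assume one compartment with first-order absorption (ka) and elimination (ke):

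- C(t) = ka/(ka − ke) × [exp(−ke·t) − exp(−ka·t)]
- Time of peak = ln(ka/ke)/(ka − ke)
- Total area to infinity = 1/ke, whatever ka is, so the true FP/whey ratio is 1.00.

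Take ke = 0.010 or 0.015 per minute, whey peaking at 45 min, and FP at 60, 75 or 90 min. The trapezoid area on the protocol's grid is 30 × (C30 + C60 + C90 + C120/2).

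Worked case, ke = 0.010:

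- Whey (ka = 0.0418): 30 × (0.5985 + 0.6143 + 0.5039 + 0.3873/2) = 57.3
- FP peaking at 60 min (ka = 0.0258): 30 × (0.4565 + 0.5488 + 0.5037 + 0.4180/2) = 51.5
- Ratio 51.5/57.3 = 0.90

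| FP peak (whey 45 min) | Area ratio, ke 0.010 | Area ratio, ke 0.015 | Sampled peak, whey / FP | FP at T120, % of its peak |
|---|---|---|---|---|
| 60 min | 0.90 | 0.85 | T60 / T60 | 76 / 74 |
| 75 min | 0.77 | 0.69 | T60 / T90 | 88 / 88 |
| 90 min | 0.65 | 0.54 | T60 / T90 | 96 / 96 |

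The deficit runs from about 10% to 46%. With sampling to 300 min on the same 30-minute grid, the ratios rise to 0.99, 0.97/0.94 and 0.92/0.86, so most of the deficit comes from the cut-off.

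**Step 3: other assumed shapes.** With absorption half-lives of 25 min against 35-100 min and clearance half-lives of 20-60 min, the ratio at 120 min is 0.49-0.93. With constant-rate absorption over 90 min against 120-240 min, it is 0.41-0.84. In 4 of the 16 first-order cases the two proteins share a sampled peak time although the ratio is 0.77-0.93. In all 16 constant-rate cases the slower protein's maximum falls on T120.

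**Step 4: could it reach significance?** With 16 completers and a two-sided paired t-test at 0.05, a 20% artefact has power 0.96 if the SD of the within-person difference is 20%, and 0.70 if it is 30%. Both SDs are assumed.

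**Step 5: do simple extra summaries help?** In the worked case the 0-60 min areas are 30 × (0.5985 + 0.6143/2) = 27.2 and 30 × (0.4565 + 0.5488/2) = 21.9, a ratio of 0.81. The 60-120 min areas are 57.3 − 27.2 = 30.1 and 51.5 − 21.9 = 29.6, a ratio of 0.98. At T120, FP is above whey (0.4180/0.3873 = 1.08). A uniform 10% deficit in extent with the same timing would give 0.90 in all three. The time of peak (T60 for both) shows none of this.

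**The case against.** Several points on the other side stand.

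- **FP is not shown to be slower.** A reader might infer it from the description of whey, but that phrase concerns whey's bioactive peptides and no FP rate is given for comparison. The gastric-emptying remark gives no direction either: Hypothesis 1 predicts similar GLP-1 stimulation, and the title of one cited study says that whey delays emptying against casein, gluten and fish protein. So the documents do not support saying that the window favours the sponsor's hypothesis; it would do so only if FP were slower.
- **Only one limb is affected.** A reader might infer that speed alone could confirm Hypothesis 1. It could not: the hypothesis also requires a similar GLP-1 and satiety hormone response, and amino acids are a secondary endpoint. Nor does the protocol say that a lower area will be reported as less complete absorption.
- **Two hours has precedent.** The Dosage section cites a pea-protein study that "stimulated insulin release over a three hour period in healthy adults", but also a soya and whey study sampled within two hours. Neither is described there for amino acids, so neither settles the window.
- **The wording is partly bounded.** The aim refers to acute effects in circulating blood, and the endpoint to availability in blood. That softens the claim without defining it as two-hour exposure.
- **Time of peak is planned.** It would show the delay in the two larger scenarios in the table, but not in the mildest. None of those scenarios has a maximum at T120; that arises under other assumed shapes.

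**Conclusion.** The mismatch is real and should be corrected, but it is a limit on interpretation and does not invalidate the trial. The protocol claims availability and bioavailability, and its planned summaries to 120 minutes cannot tell slower appearance from less complete absorption or from lower content. The illustrative size is a 10-46% lower area with no true difference in extent. That range rests wholly on assumed kinetics (one compartment, whey peak at 45 min, FP peak at 60-90 min, elimination 0.010-0.015 per minute) and is not an estimate for these products. It would be small if the two proteins appear at similar speeds.

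**What to change.** 1. In the aim, Questions 1 and 2, Hypothesis 1 and the secondary endpoint, replace availability or bioavailability with *plasma amino acid appearance over 0-120 min*.
2. State that a lower 0-120 min area will not by itself be interpreted as less complete absorption or lower digestibility.
3. Beside the iAUC, report T120 minus T0 and the partial areas 0-60 and 60-120 min for each drink. If the planned iAUC at 30, 60, 90 and 120 min means cumulative areas, most of this is already available by subtraction; the protocol should say so.
4. Report a maximum seen at T120 as *at or after 120 min*, not as a peak time.

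A rule that allows an availability reading only once both curves are back near T0 should not be added. In the scenarios of Step 2 whey itself is still at 53-61% of its peak at T120, so the rule would block that reading every time and would not discriminate.

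The change needs no new samples or visits. It costs protocol wording, a few extra summaries and a narrower claim on a secondary endpoint.
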